### 12.3 SLIT LAMP BIOMICROSCOPY

A slit lamp examination will be performed and the following structures will be assessed for pathology:

- Eyelids and lashes (i.e., meibomian glands, lid margin, puncta, lashes)
- Cornea (NEI grading for staining)
- Conjunctiva
- Anterior chamber
- Iris

#### 12.3.1 COLLARETTE GRADING

Grade	Clinical Interpretation
0	0 to 2 lashes have collarettes per eyelid
1	3 to 10 lashes have collarettes per eyelid
2	More than 10 but less than $\frac{1}{3}$ of lashes have collarettes per eyelid
3	$\frac{1}{3}$ or more but less than $\frac{2}{3}$ of lashes have collarettes per eyelid
4	$\frac{2}{3}$ or more of lashes have collarettes per eyelid

0.5 unit increments ARE NOT allowed

#### 12.3.2 LID MARGIN ERYTHEMA GRADING

[figure not shown]
[figure not shown]
Erythema of the eyelid margin should be graded on a scale from 0 (normal) to 3 (severe erythema).

Grade	Severity	Clinical Interpretation
0	Normal	Normal age-related lid coloration
1	Mild	Pink capillary involvement along the lid edge, no patches of confluent capillary redness throughout the lid edge
2	Moderate	Deep pink or red confluent capillary redness present locally along the lid edge
3	Severe	Deep red, diffuse confluent capillary redness present along the lid edge

[figure not shown]
0.5 unit increments ARE NOT allowed

---

[figure not shown]
#### 12.3.3 CORNEAL FLUORESCEIN STAINING

[figure not shown]

## 12.5 DEMODEX COUNT

## 12.6 INTRAOCULAR PRESSURE

[REDACTED]

[REDACTED]

[REDACTED]

#### 12.10 URINE PREGNANCY TEST

[REDACTED]

[REDACTED]

[REDACTED]

15.3 Eyelid Photos	36
15.4 Drop Comfort.....	36
16. Interim Analyses.....	37
17. Changes from Protocol-Stated Analyses	37

List of Abbreviations

Abbreviation	Definition
ADaM	Analysis Data Model
AE	Adverse Event
ANCOVA	Analysis of Covariance
ATC	Anatomical Therapeutic Chemical
BID	Bis in die (Two Times a Day)
CDVA	Corrected Distance Visual Acuity
CI	Confidence Interval
COVID-19	Coronavirus Disease 2019
CS	Clinically Significant
eCRF	Electronic Case Report Form
EDC	Electronic Data Capture
ETDRS	Early Treatment Diabetic Retinopathy Study
FAS	Full Analysis Set
ICF	Informed Consent Form
ICH	International Conference on Harmonisation
IOP	Intraocular Pressure
IRB	Institutional Review Board
IRT	Interactive Response Technology
logMAR	Logarithm of the Minimum Angle of Resolution
LS	Least Squares
MCMC	Markov Chain Monte Carlo
MedDRA	Medical Dictionary for Regulatory Activities
MI	Multiple Imputation
NCS	Not Clinically Significant
OD	Oculus dexter (Right Eye)
OS	Oculus sinister (Left Eye)
PDF	Portable Document Format
PP	Per Protocol
PT	Preferred Term
RDC	Remote Data Capture
RTF	Rich Text Format
SAE	Serious Adverse Event
SAP	Statistical Analysis Plan
SD	Standard Deviation
SDC	Statistics & Data Corporation
SDTM	Study Data Tabulation Model
SE	Standard Error
SOC	System Organ Class
TEAE	Treatment-Emergent Adverse Event
TP-03	Lotilaner Ophthalmic Solution, 0.25%
WHODrug	World Health Organization Drug Dictionary

1. Introduction

The purpose of this statistical analysis plan (SAP) is to describe the planned analyses and reporting for protocol TRS-010, Version 4.0 dated 09DEC2021.

This SAP is being written with due consideration of the recommendations outlined in the most recent International Conference on Harmonisation (ICH) E9 Guideline entitled Guidance for Industry: Statistical Principles for Clinical Trials and the most recent ICH E3 Guideline entitled Guidance for Industry: Structure and Content of Clinical Study Reports.

This SAP describes the data that will be analyzed and the subject characteristics, efficacy, and safety assessments that will be evaluated. This SAP provides details of the specific statistical methods that will be used. The statistical analysis methods presented in this document will supersede the statistical analysis methods described in the clinical protocol. If additional analyses are required to supplement the planned analyses described in this SAP, they may be completed and will be identified in the clinical study report.

2. Study Objectives

The overarching objective of this study is to demonstrate the safety and efficacy of TP-03, 0.25%, for the treatment of *Demodex* blepharitis.

The primary objective of this study is to demonstrate the safety and efficacy of lotilaner ophthalmic solution (TP-03), 0.25%, compared to its vehicle as a cure of mild to severe *Demodex* blepharitis.

The secondary objectives of this study are:

- To demonstrate the efficacy of TP-03, 0.25%, to eradicate *Demodex* mites from the eyelid margin;
- To demonstrate the efficacy of TP-03, 0.25%, to eliminate collarettes and erythema from the eyelid margin; and
- To demonstrate the efficacy of TP-03, 0.25%, to eliminate erythema from the eyelid margin.

2.1 Primary Endpoint

The primary efficacy endpoint is cure based on a collarette score of 0 for the upper eyelid of the analysis eye at Day 43. The primary safety endpoint is treatment-related adverse effects.

2.2 Secondary Endpoints

The secondary efficacy endpoints are:

- *Demodex* mite eradication (mite density of 0 mites/lash) from the analysis eye, at Day 43

- Composite cure based on collarette score (0) and erythema score (0) for the upper eyelid of the analysis eye at Day 43
- Erythema cure based on erythema score (0) for the upper eyelid of the analysis eye at Day 43

2.4 Safety and Other Assessments

The safety and other assessments to be performed include the following:

- Adverse events (AEs)
- Corrected distance visual acuity (CDVA)
- Slit lamp biomicroscopy assessment
- Corneal staining
- Intraocular pressure (IOP) measurement

2.5 Statistical Hypotheses

The null and alternative hypotheses, based on the primary efficacy endpoint, are:

H_0 : The proportion of subjects cured at Day 43 based on collarette score of 0 for the upper eyelid of the analysis eye, by treatment with TP-03, 0.25%, is \leq the proportion cured by treatment with vehicle.

H11: The proportion of subjects cured at Day 43 based on collarette score of 0 for the upper eyelid of the analysis eye, by treatment with TP-03, 0.25%, is > the proportion cured by treatment with vehicle.

The secondary efficacy hypotheses for *Demodex* eradication are:

H_{02} : The proportion of subjects with *Demodex* eradicated at Day 43 (mite density of 0 mites/lash) in the analysis eye by treatment with TP-03, 0.25%, is \leq the proportion with *Demodex* eradicated by treatment with vehicle.

H_{12} : The proportion of subjects with *Demodex* eradicated at Day 43 (mite density of 0 mites/lash) in the analysis eye by treatment with TP-03, 0.25%, is $>$ the proportion with *Demodex* eradicated by treatment with vehicle.

The secondary efficacy hypotheses for composite of collarette and erythema cure are:

H_{03} : The proportion of subjects with a composite cure, collarette score of 0 and erythema score of 0, for the upper eyelid of the analysis eye at Day 43 by treatment with TP-03, 0.25%, is \leq the proportion with a composite cure by treatment with vehicle.

H_{13} : The proportion of subjects with a composite cure, collarette score of 0 and erythema score of 0, for the upper eyelid of the analysis eye at Day 43 by treatment with TP-03, 0.25%, is $>$ the proportion with a composite cure by treatment with vehicle.

The secondary efficacy hypotheses for erythema cure are:

H_{04} : The proportion of subjects with an erythema cure, score of 0, for the upper eyelid of the analysis eye at Day 43 by treatment with TP-03, 0.25%, is \leq the proportion with an erythema cure by treatment with vehicle.

H_{14} : The proportion of subjects with an erythema cure, score of 0, for the upper eyelid of the analysis eye at Day 43 by treatment with TP-03, 0.25%, is $>$ the proportion with an erythema cure by treatment with vehicle.

2.6 Estimands

The primary comparisons in this trial will be between active drug versus vehicle at Day 43 in the Full Analysis Set (FAS, as outlined in [Section 7.1](#)) using the following estimands.

- Population: subjects with *Demodex* Blepharitis defined through enrollment criteria
- Endpoint:
 - Proportion of subjects cured, based on a collarette score of 0, for the upper eyelid of the analysis eye at Day 43
 - Proportion of subjects with their *Demodex* mites eradicated, mite density of 0 mites/lash, from the analysis eye at Day 43.
 - Proportion of subjects that achieved a composite cure, based on collarette and erythema scores of 0, for the upper eyelid of the analysis eye at Day 43.

- Proportion of subjects that achieved an erythema cure, based on erythema score 0, for the upper eyelid of the analysis eye at Day 43
- Intercurrent event:
 - Discontinuation of study medication and non-optimal compliance is ignored [treatment policy strategy].
 - Withdrawal due to lack of efficacy or AEs: missing data will be imputed as failure [hypothetical strategy].
 - Missing data without withdrawal or withdrawal due to reasons other than lack of efficacy or AEs: missing data will be imputed employing Multiple Imputation (MI) using randomized treatment-based Markov Chain Monte Carlo (MCMC) methodology [hypothetical strategy].
- Population-level summary:
 - Difference in proportion of subjects cured, based on a collarette score of 0 for the upper eyelid of the analysis eye, at Day 43
 - Difference in proportion of subjects with their Demodex mites eradicated, mite density of 0 mites/lash, from the analysis eye at Day 43.
 - Difference in proportion of subjects that achieved a composite cure, based on collarette and erythema scores of 0 for the upper eyelid of the analysis eye, at Day 43.
 - Difference in proportion of subjects that achieved an erythema cure, based on erythema score 0 for the upper eyelid of the analysis eye, at Day 43

If the percentage of data missing at Day 43 due to discontinuation of study medication and non-optimal compliance exceeds 2%, these missing data will be imputed as failures and the primary efficacy analysis will be repeated in a separate analysis.

Sensitivity analyses on the primary efficacy endpoint and secondary efficacy endpoints are described in the Efficacy Analysis section ([Section 13](#)).

2.7 Study Milestones for Analyses

Two study milestones for analysis purposes are defined based on subject completion of key visits:

Milestone 1 will be met after all subjects have completed efficacy assessment visits: The last efficacy measures are scheduled at Day 57 for Cohort 1 subjects and Day 43 for Cohort 2 subjects. Milestone 1 will be used to assess efficacy and safety during the on-treatment interval, which is defined as screening through Day 43/57. After this milestone is met, the database will be cleaned, locked, unmasked and all tables, listings, and figures will be produced with data for the on-treatment interval (excluding Day 90). However, all available data for adverse events and concomitant medications and procedures with start dates within the on-treatment interval will be included in the tables and listings, and thus AEs or concomitant medications or procedures with start dates during

the on-treatment interval and end dates after Day 43/57 will be shown in Milestone 1 tables and listings.

Milestone 2 will be met after all eligible subjects have completed safety and other assessments at Day 90. Milestone 2 will be used to assess safety during the post-treatment interval, which is defined as after Day 43/57 through Day 90. After this milestone is met listings and tables for subject disposition, protocol deviations, analysis population inclusion, subjects effected by COVID-19 and the assessments performed at Day 90 (slit-lamp biomicroscopy, endothelial cell density, CDVA) will be re-run to include the Day 90 assessments. Adverse event and concomitant medication and procedure listings will be re-run to include the Day 90/post-treatment interval data, as will listings for any safety or efficacy endpoints collected during an unscheduled visit during the post-treatment interval. The tables for the AEs and concomitant medications and procedures with start dates during on-treatment interval will also be re-run and updated to include the Day 90/post-treatment interval data. Separate tables for AEs and concomitant medications and procedures with start dates after milestone 1, during the post-treatment period, will be generated for Milestone 2.

3. Study Design and Procedures

3.1 General Study Design

This Phase 3 study is a randomized, controlled, multicenter, double-masked, parallel trial to evaluate the safety and efficacy of TP-03, 0.25%, for the treatment of *Demodex* blepharitis.

A subject's participation is to start with screening at Day -14 to 1. At the Screening visit, potential subjects will be evaluated for eligibility. Prior to performing any study specific procedures, potential subjects must provide informed consent using the current Institutional Review Board (IRB) approved informed consent form (ICF). Potential subjects who meet all eligibility criteria can proceed directly to the Day 1 procedures or the Day 1 visit can be scheduled within the next 14 days. If a subject does not come in for the Day 1 visit within 14 days, the Screening visit procedures must be repeated. If the subject is considered eligible for the study at the end of the Screening visit, the subject will be randomized at Day 1 to receive one of the following treatments administered bilaterally two times a day (BID) for approximately 43 days: TP-03, 0.25%, or the TP-03 vehicle. Subjects in Cohort 1 (signed informed consent on or before 21 October 2021) will complete an observational study assessment visit (Day 57) while Cohort 2 subjects (signed informed consent on 22 October 2021 or later) will not complete a Day 57 visit. Subjects from both cohorts at sites using specular microscopy will also attend a safety assessment including endothelial cell counts and end of study visit (Day 90).

For subjects reporting for an unscheduled visit, assessments may be performed at the discretion of the investigator. At a minimum, CDVA and the occurrence of any AEs should be assessed.

In this study, subjects will be instructed to administer a single drop of the study product BID (morning and evening) in each eye. The treatment period will be for approximately 43 days.

At Day 1, site staff will supervise the subject's first dose of the study medication. The remaining doses of the study medication will be administered by the subjects at home.

During waking hours, if a dose is missed in the morning, subjects will be instructed to administer the drop if it is at least an hour prior to the second dose of the day. If it is less than an hour, the subject should simply dose the second drop of the day.

Study day will be referred to in all tables and listings. Table 1 shows the planned study day and the acceptable window per protocol for each study visit:

Table 1. Study Visit Windows

Planned Study Day	Day Window Per Protocol
Day -14 to Day 1 (Screening)	N/A
Day 1 (Randomization)	N/A
Day 8	± 3 Days
Day 15	± 3 Days
Day 22	-3 / +4 Days
Day 43	-3 / +7 Days
Day 57 (Cohort 1 subjects only)	-6 / +14 Days
Day 90 (selected sites only)	± 14 Days

3.2 Schedule of Activities

The Schedule of Activities is provided in Table 2.

Table 2. Schedule of Activities

Procedures	Screening Day -14 to 1	Enrollment/initiation of Study Treatment Day 1	Day 8 ± 3 days	Day 15 ± 3 days Day 22 -3/44 days	Day 43 -3/7 days	Day 57 -6/+14 days (Cohort 1 only)	Day 90 ± 14 days (only at sites performing specular microscopy)
Informed consent	X						
Demographics	X						
Medical/ophthalmic history	X						
Concomitant medication review	X	X ^a	X	X	X	X	X
Corrected distance visual acuity (CDVA)	X	X ^a	X	X	X	X	X
Slit lamp biomicroscopy	X	X ^a	X	X	X	X	X
Collarette grading; erythema	X		X	X	X	X	
Corneal staining		X	X	X	X	X	
Intraocular pressure		X			X	X	
Demodex count		X		X	X	X	
Urine pregnancy test ^b	X				X		
Randomization		X					
Dispense study drug; diary		X					
Collection and review of participant diary			X	X			
Collection of study drug and return to participant			X	X			
Adverse event review and evaluation		X	X	X	X	X	X
Collect study drug; diary					X		
Study exit					X ^c	X ^d	X ^e

a: If the Screening and Day 1 visits are completed on the same day, this test does not have to be repeated.

b: Women of childbearing potential

c: Study exit for Cohort 2 subjects if site is not performing specular microscopy

d: Study exit for Cohort 1 subjects if site is not performing specular microscopy

e: Study exit for subjects at sites performing specular microscopy

4. Study Treatments

4.1 Method of Assigning Subjects to Treatment Arms

All subjects, investigators, study personnel involved with the conduct of the study and Sponsor will be masked with regard to treatment assignments.

A balanced (1:1) randomization will be used for this study. A computer-generated blocked randomization schedule will be generated by [REDACTED]. [REDACTED] will use the randomization schedule to package the study drug. The labelled study drug will be shipped to the US distribution center for distribution to the clinical sites.

While undergoing Screening, potential study subjects will be identified by their initials and screening number in the screening and enrollment log. All subjects screened for the study who sign an ICF will be assigned a 3-digit screening number. Screening numbers will be assigned in a sequential order beginning with 301. A dash (-) will be used in place of the middle initial for potential subjects who have no middle name.

If a potential study subject has provided written informed consent and met all eligibility criteria, the subject is considered eligible to participate. If the potential subject elects to participate in the study, they can continue with the Day 1 procedure or be scheduled to return for Day 1. At Day 1, they will be dispensed the next available study drug bottle from the current site inventory by the Interactive Response Technology (IRT) system ([REDACTED]), which uses block stratification by site. The subject will be randomized and receive their assigned study drug at the completion of the Day 1 visit and the subject will be considered enrolled in the study. The subject will be assigned a unique identification number consisting of their site number followed by a hyphen and then the screening number.

4.2 Masking and Unmasking

Throughout the study, the subject, investigator, site personnel performing study assessments and Sponsor will remain masked to the study medication. The active and vehicle control ophthalmic solutions will be indistinguishable in appearance and will be distributed in bottles identical in appearance.

Treatment assignments should only be unmasked if needed for proper care of the subject. Sites will be provided instructions on the procedure to be followed to unmask the treatment assignment for a subject. Inadvertent unmasking will be reported to the sponsor and IRB as required.

The IRT system will also be used to dispense any replacement bottles needed by a subject if they lose their current bottle or it becomes damaged.

5. Sample Size and Power Considerations

A total sample size of 300 subjects (150 subjects per arm) yields approximately 99% power to establish superiority of TP-03 to vehicle in the subjects meeting the primary efficacy endpoint assuming a response rate of 80.0% in TP-03 and 15.8% for vehicle treatments, respectively, using Pearson chi-squared to test a one-sided hypothesis with a significance level of 0.025. Response rates for sample size calculations are

based upon a prior outside United States clinical study of TP-03, 0.25%, and vehicle for the treatment of *Demodex* blepharitis.

Based on the results of a more recent Phase 2b/3 study, TRS-009 (Saturn-1), with a response rate of 44.0% for the TP-03 treatment group and 7.4% for the vehicle treatment group, a total sample size of 300 subjects still provides greater than 99% power.

Similarly, 300 subjects (150 subjects per arm) yields 99% power to establish superiority of TP-03 to vehicle treatment in the proportion of subjects with *Demodex* eradicated and 99% power for the proportion of subjects with a composite of collarette and erythema cure at Day 43 assuming a response rate of 73.3% in TP-03 and 21.1% in vehicle for *Demodex* eradication and 73.3% in TP-03 and 10.5% in vehicle for composite cure using Pearson chi-squared to test a one-sided hypothesis with a significance level of 0.025.

Based on the results from TRS-009 (Saturn-1) with response rates of 67.9% in the TP-03 treatment group and 17.6% in the vehicle treatment group for *Demodex* eradication and 13.9% in the TP-03 treatment group and 1.0% in the vehicle treatment group for composite cure, a sample size of 300 subjects still provides greater than 99% power to demonstrate superiority of TP-03 to vehicle for each endpoint.

For erythema cure, a sample size of 300 subjects will provide 88% power to demonstrate superiority of TP-03 to vehicle at a one-sided significance level of 0.025 based on the results from TRS-009 (Saturn-1), response rate of 19.1% for TP-03 and 7.4% for vehicle.

The study will be considered a success and TP-03, 0.25% will be considered superior to vehicle in clinical cure if H_{01} is rejected in favor of H_{11} . With this sample size, the study will have > 95% power to claim success for clinical cure. A closed hierarchical testing structure will be used such that the analysis will first be performed for the primary efficacy endpoint. Only if the null hypothesis for the primary efficacy endpoint is rejected will analyses be performed for the three secondary efficacy endpoints using the Hochberg testing strategy. Additional details can be found in [Section 8.5](#). If in addition to success for clinical cure, the largest p-value among the secondary endpoints allows for rejection of the null hypothesis in favor of the alternative hypothesis at a significance level of 0.025 then the study will also claim superiority of TP-03, 0.25%, to vehicle for all secondary endpoints. If the study cannot reject the null hypothesis for the secondary endpoint with the largest p-value, the next largest p-value among the remaining two endpoints will be evaluated at a significance level of 0.0125. The study will claim superiority of TP-03, 0.25%, to vehicle for both remaining endpoints if the null hypothesis is rejected in favor of the alternative hypothesis. If the study cannot reject the null hypothesis, the remaining secondary endpoint will be evaluated at a significance level of 0.0083. If the null hypothesis is rejected in favor of the alternative, the study will be able to claim success for the remaining secondary endpoint.

Accounting for a 30% discontinuation, approximately 209 subjects per arm (approximately 418 total) will be randomized. The planned enrollment is much greater than typically planned to achieve 300 completed

subjects due to concerns regarding the impact of COVID-19 and the possibility that up to two sites may be unable to complete the study.

6. Data Preparation

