8.5 Adjustments for Multiplicity

A closed hierarchical testing structure will be used where the analysis will be performed for the primary efficacy endpoint and, only if successful, the analysis will be performed for the three secondary efficacy endpoints using the Hochberg testing strategy. Specifically, if the null hypothesis, H_{01} , is rejected at a one-sided α of 0.025, the study will be considered a success for clinical cure and the family of three secondary efficacy endpoints will be tested using the Hochberg testing strategy with a familywise α of 0.025. If the secondary endpoint with the largest p-value is significant at the 0.025 level, then all three secondary endpoints will be declared statistically significant. If the secondary endpoint with the largest p-value is not significant at the 0.025 level, then the secondary endpoint with the second largest p-value will be tested at the 0.0125 level. If this secondary endpoint is significant at the 0.0125 level, then it and the endpoint with the smallest p-value will be declared statistically significant. If not, the endpoint with the smallest p-value will be tested at the 0.0083 level. If the null hypothesis, H_{01} is not rejected at a one-sided α of 0.025 testing will stop and the three secondary efficacy hypotheses will not be tested.

9. Disposition of Subjects and Protocol Deviations

Subject disposition will be presented in terms of the numbers and percentages of subjects who were randomized to masked study medication with subcategories for those who did or did not dose with the masked study medication; those who were included in the FAS, COVID-19, PP, and Safety sets; and those who completed the study and discontinued from the study. Subjects who do not discontinue from the study will be considered study completers. Subject enrollment and disposition will be summarized by treatment arm and completion/discontinuation will be summarized by treatment arm and site. Percentages will be calculated using randomized subjects as the denominator unless otherwise specified.

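### The 88% power stated for erythema cure does not reproduce with 300 subjects: the Pearson chi-squared formula gives about 85%, and other usual calculations give 86–87%

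*SAP*

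**What the plan says.** SAP Section 5 (Sample Size and Power Considerations) works from 300 subjects, 150 per arm, and SAP Section 4.1 confirms the allocation: "A balanced (1:1) randomization will be used for this study". For the primary endpoint, mite eradication and composite cure, Section 5 gives power figures based on the study outside the United States, calculated "using Pearson chi-squared to test a one-sided hypothesis with a significance level of 0.025". It then says that the Saturn-1 rates still give more than 99% power for those three endpoints.

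Erythema cure has a single power statement: "For erythema cure, a sample size of 300 subjects will provide 88% power to demonstrate superiority of TP-03 to vehicle", at one-sided 0.025, based on a "response rate of 19.1% for TP-03 and 7.4% for vehicle" in Saturn-1. This sentence names no test, formula or software.

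SAP Section 8.5 tests the three secondary endpoints by the Hochberg procedure once the primary has succeeded. The largest p-value is compared with 0.025. If it fails, the second largest is compared with 0.0125: "If this secondary endpoint is significant at the 0.0125 level, then it and the endpoint with the smallest p-value will be declared statistically significant".

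Protocol Section 9.2 gives no power figure for erythema cure.

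**The concern.** The sentence supplies everything needed to recompute its own result: sample size, rates, alpha and sidedness. It is also the only endpoint-specific power in the section below 99%. The other figures are so high that the choice of method hardly shows in them. This one is sensitive enough to be checked, and a quick check falls short of 88%.

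Erythema cure is the least powered member of the Hochberg family, so it largely decides whether all three secondary claims can be made at the first step (0.025). The SAP implies a 12% chance of missing erythema cure at that level. If the true power is lower, that risk is understated, and because no method is named a reader cannot tell where 88% came from.

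**Working it through.** **Inputs** (SAP Sections 4.1 and 5): n = 150 per arm; p1 = 0.191 (TP-03); p2 = 0.074 (vehicle); difference 0.117; one-sided alpha 0.025, so z = 1.96.

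**Pearson chi-squared formula** (pooled variance under the null, separate variances under the alternative):

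- Mean rate: (0.191 + 0.074)/2 = 0.1325.
- Null standard error: √(2 × 0.1325 × 0.8675/150) = 0.03915.
- Alternative standard error: √((0.191 × 0.809 + 0.074 × 0.926)/150) = √((0.1545 + 0.0685)/150) = 0.03856.
- Power: Φ((0.117 − 1.96 × 0.03915)/0.03856) = Φ(1.044) = **85.2%**.

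**Unpooled normal formula:** Φ(0.117/0.03856 − 1.96) = Φ(1.074) = **85.9%**.

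**Arcsine formula:** h = 2·asin√0.191 − 2·asin√0.074 = 0.3536; Φ(0.3536 × √75 − 1.96) = Φ(1.102) = **86.5%**.

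**Exact enumeration** (sum of the binomial probabilities of all outcome pairs in which the statistic exceeds 1.96):

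- Pearson statistic: **86.3%**; a simulation of 2 million trials also gave 86.3%.
- Unpooled standard error: **86.6%**. With complete data this is the closest match to the risk-difference analysis with its asymptotic standard error coded in SAP Section 13.2.

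**Other methods tried:** likelihood-ratio approximation 85.9%, exact likelihood ratio 86.6%, t test 85.6%, mid-p 85.7%, Fisher's exact 82.6%, log-odds 82.4%, continuity-corrected 80.8–81.8%. None exceeds 86.6%.

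**Could rounding of the input rates explain it?** The rates are printed to one decimal, so TP-03 lies between 19.05% and 19.15% and vehicle between 7.35% and 7.45%.

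| Method | Range over rounding |
|---|---|
| Pearson formula | 84.6–85.8% |
| Exact, unpooled | 86.0–87.2% |

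The best case is 87.2%, which rounds to 87%.

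**Could another sample size explain it?** The only other one in the section is 209 per arm, which gives 94.4% by the Pearson formula. The smallest n per arm for the stated power is:

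| Method | For 88% | For 87.5% |
|---|---|---|
| Pearson formula | 164 | 161 |
| Unpooled formula | 161 | 158 |
| Arcsine | 158 | 155 |
| Exact Pearson | 158 | 156 |
| Exact unpooled | 156 | 154 |

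All exceed 150.

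**Do the other Saturn-1 figures reproduce?** Yes. By the Pearson formula at 150 per arm, composite cure (13.9% against 1.0%) gives 99.1%. Collarette cure (44.0% against 7.4%) and eradication (67.9% against 17.6%) both exceed 99.9%. Erythema cure is the one Saturn-1 power that does not match.

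**Effect on the Hochberg steps.** The chance of missing erythema cure at 0.025 is 14.8% by the Pearson formula (100 − 85.2) and 13.4–13.7% by exact enumeration, against the 12% implied. If it misses, the other two are tested from 0.0125, where the Pearson formula gives 98.1% for composite cure and above 99.9% for eradication.

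**The case against.** The strongest reply has three parts.

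First, the shortfall depends on the method. The 2.8-point gap belongs to the pooled normal approximation. The exact power of the Pearson test is 86.3%, which is 1.7 points below 88%, and arcsine, exact unpooled and exact likelihood-ratio power also come within two points.

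Second, the erythema sentence names no test. Pearson chi-squared is stated for the other endpoints, so using it as the benchmark here is an inference, and 85% is not the only defensible replacement.

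Third, nothing in the design depends on the figure. Protocol Section 4.1 bases the sample size mainly on safety. About 418 subjects are to be randomized, and the secondary analyses use all of them, with missing data imputed, so actual power may well exceed the 300-subject figure; 94.4% with complete data at 209 per arm is an upper bound. The input rates are also point estimates from a single trial, and planning rates have moved far more than this between studies: composite cure on TP-03 was 73.3% in the earlier study and 13.9% in Saturn-1.

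The second and third parts stand as limits on the remedy and the consequence. They are why the sponsor should be free to name another method, and why no design change follows. They do not rescue the figure. The sentence is explicitly about 300 subjects, and being within two points does not reproduce a power stated to the whole percent when no method tried rounds to it.

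**Conclusion.** The concern holds. With 150 per arm, 19.1% against 7.4% and one-sided 0.025, power for erythema cure is 85.2% by the Pearson formula and up to 86.6% by exact enumeration. The stated 88% is therefore too high by 1.4 to 2.8 points, and favourable rounding of the rates does not close the gap.

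This rests on the SAP's own inputs, equal allocation and complete data on 300 subjects. The one inference is that the Pearson method named elsewhere in the section also applies to erythema cure; the conclusion does not depend on it, since every alternative tried also falls short. The practical effect is small and confined to one planning figure for one secondary endpoint. It alters no analysis, p-value or claim.

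**What to change.** In SAP Section 5, replace the 88% in the erythema sentence with *approximately 85% power (Pearson chi-squared, 150 subjects per arm)*. If another method was used, name it and give the figure it produces, which for the alternatives that come closest to 88% is 86–87%.

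The cost is one figure and a method name in one sentence. The protocol needs no change on this point, and enrolment, test, alpha and the Hochberg procedure are unaffected.
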